The clinician version of the SCID is a brief structured interview for major Axis I disorders in DSM.¹¹³ The CIWA-Ar is a 10-item, clinician-rated scale with a range from 0-67 that assesses alcohol withdrawal symptoms.¹¹⁴ The HRSD₁₇ is an observer-rated measure of depressive symptomatology.¹¹⁵ The IDS-SR₃₀ is a 30-item self-report scale of depressive symptom severity.¹¹⁶⁻¹¹⁹ YMRS is an 11-item, observer-rated measure of manic symptoms.¹²⁰ The HRSA is a 14-item observer-rated assessment of anxiety symptoms.¹²¹ PACS is a 5-item. self-report measure that includes questions about alcohol craving.¹²² The Short Index of Problems (SIP) is a 15-item self-rated measure that assesses recent and lifetime alcohol-related problems. The SAFTEE is a 56-item self-rated scale assessing a variety of somatic symptoms. TLFB is a method for assessing recent drinking, in which participants retrospectively estimate daily alcohol consumption over a period of time ranging from 7 days to 24 months.^{111, 112} The Treatment Impressions Inventory (TII) is a survey about your feelings and impressions about medical treatment. The World Health Organization/University of California at Los Angeles Auditory-Verbal Learning Test (WHO-UCLA AVLT) is designed to test verbal learning and memory. The Golden Stroop Color Word Test measures ease with which a person shifts perceptual sets to conform to changing demands and suppresses habitual responses in favor of non-dominant ones.¹²⁴ Trail Making Test (TMT) Parts A and B are tests for executive functioning, attention, sequencing, visual search, and motor function, with mental sequencing additionally required for Part B.¹²⁴ Columbia Suicide Severity Rating Scale (CSSRS) is a structured interview and rating scale used to measure suicidal ideation. An exit survey to evaluate participant's perception of in-person vs. virtual visits will be administered at week 12 or the last study visit in the event of early discontinuation.

Table 2. Assessment Schedule

														Wk
												Wk	Wk	12
Instrument	BL1	BL2	Wk 1	Wk 2	Wk 3	Wk 4	Wk 5	Wk 6	Wk 7	Wk 8	Wk 9	10	11	Final

SCID	Х													
YMRS, HRSD17, CSSRS, TLFB, CIWA-Ar, UDS	х	х	х	х	х	х	х	х	х	х	х	х	х	х
HRSA IDS-SR30, PACS, SAFTEE		х	х	х	х	х	х	х	х	х	х	Х	х	х
CBC, metabolic panel including AST, ALT (+ GGT, CDT), UPT	х							х						х
Lipid panel	х													х
Neurosteroid and choline levels		х												Х
Optional genetics blood draw		Х												

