respectively, and the limit of detection was 1 pg for both. With participant consent, DNA will also be obtained for future analysis. Plasma samples for DNA will be coded and sent to UT Southwestern McDermott Center for Human Growth and Development. Samples will have their DNA banked in a secure freezer with coded identification that will not include any personal identifiers such as the subject's name. Samples will begin to be analyzed when 50% (100) have been collected. When candidate genes have been suitably refined, and SNP chips become commercially available, appropriate pathways and candidate genes will be assessed via SNP chips and associated with previously assessed behaviors, personality styles, and/or biologic responses. *The neurosteroid and choline levels are essential as biomarkers and predictor of clinical response, as well as to address exploratory aim 5.*

3.3.c. Statistical Analyses Plan

Randomization: A statistician will randomize participants, stratifying by baseline drinks per drinking day of ≥ 8 and < 8 (based on use patterns in our prior studies).

General Analytic Plan: This is a study utilizing a two-stage adaptive trial design with one planned interim analysis (at end of the first stage). Two stages consist of a treatment selection stage (Stage 1) and a stage of early efficacy confirmation of the selected treatment(s) (Stage 2).¹³¹ In **Stage 1**, participants will be randomized at a 1:1:1 ratio to receive one of the three treatments: placebo, citicoline, and pregnenolone. After 99 participants have completed the duration of treatment (completer, dropout, discontinued) an interim analysis will be performed based on the number of drinks per drinking day (primary outcome measure). Based on the interim analysis, adaptations such as stopping the trial early, re-estimating the sample size, or a different randomization scheme may be applied as recommended by the independent DSMB.

Note that a precision analysis (i.e., a confidence interval approach) will be considered for treatment selection at Stage 1.¹³¹ To evaluate the relative risk of making wrong decision and increase confidence in not making wrong decision at Stage 1, sensitivity analyses based on predictive confidence interval of the true difference, which is calculated using the observed difference, at interim analysis will be conducted for treatment selection. At the end of Stage 1, one of the following decisions will be made based on the following principles:

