- 1. The trial will be stopped if neither active treatment appears to be effective (both active treatment effect sizes are smaller than a minimum clinically important difference, defined as an effect size of 0.25).
- 2. The trial will continue to Stage 2, if there is evidence (based on precision analysis i.e., a smaller interval width) that at least one treatment from the interim analysis at end of Stage 1 is more effective than placebo. If both treatments appear to be effective in Stage 1 then the trial will continue with three-arms. Findings from the interim analysis may result in change in sample size required for achieving statistical

significance at a desired power. At the end of Stage 2, data collected from both stages will be combined for a final analysis. Depending on the results of the interim analysis, blinded sample size re-estimation may be performed per recommendation from the DSMB.

Stage 2 will be a two-arm (assuming that only one promising treatment is retained) randomized study comparing the selected treatments from Stage 1 versus the placebo. At the end of the Stage 2, the selected treatment will be compared with placebo using the number of drinks per drinking day as the primary outcome measure. At each stage, the primary efficacy analysis will be performed based on the intention-to-treat (ITT) population, defined as all randomized participants who have at least one follow-up evaluation regardless of their compliance with the protocol. In case of substantial numbers of protocol violations, a per-protocol analysis may be done to determine whether they influence the conclusions. At end of Stage 2 (or end of trial), a clinical superiority test may be performed after non-inferiority has been established, without paying any statistical penalty.

Sample size re-estimation: Sample size re-estimation will be performed based on the number of drinks per drinking day as the primary outcome measure. Sample size calculations will be performed as follows:¹³²

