At Stage 1, we will recruit 99 subjects (i.e., 33 subjects per arm) with 1:1:1 treatment allocation ratio, which provides clinically meaningful minimum *effect size of 0.25 between each treatment arm and placebo with* a two-sided test at the 5% level of significance. After review of interim data, an additional 100 subjects at 1:1 ratio will be recruited at Stage 2. If the effect size for *both* medications is at least 0.50 at interim analysis then we will have 81.4% power with 66 participants per arm and the study will continue with three treatment arms. To summarize: 1) If neither treatment has an effect size of at least 0.25 at interim analysis then the trial is discontinued. *This effect size was selected because it is a clinically meaningful value. Naltrexone has an average effect size of approximately 0.15-0.20 in clinical trials for alcohol dependence.*¹³³ *Thus, a useful new treatment for alcohol dependence should at least have a larger effect size than the standard treatment. This effect size of 0.25 is also an effect size at interim analysis that provides a reasonable likelihood of a significant difference from placebo at study completion assuming some increase in effect size as more participants are*

enrolled and the variance of the data decreases. 2) If one treatment has an effect size of at least 0.25 then the trial continues dropping the less effective treatment (two-arm study of one medication vs. placebo). 3) If both treatments have an effect size of at least 0.50 then neither treatment is dropped and the trial continues as a three-arm trial (both medications vs. placebo). This assumes that the DSMB assessment determines that the selected treatment(s) has an adequate safety and tolerability profile to continue the trial. We anticipate that the interim analysis will take place at approximately month 26 of the study. As an incentive to enroll quickly and avoid prolonging the study, we will mandate that an interim analysis take place by month 34 even if fewer than 99 participants have been enrolled. All interim analysis decisions will be made in consultation with the NIAAA program official and DSMB.

Statistical Methods:

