The primary analysis is to assess between-group differences in alcohol use measures including drinks per drinking day (primary outcome measure), heavy drinking days, and drinking days using Generalized Estimation Equations (GEEs) analysis with a site effect as a cluster. GEE model has been used in a prescription drug abuse treatment study with multiple site adaptive design (Weiss et al., 2010).¹⁰⁶ Point estimates of the difference in the average of the number of drinks per drinking day between treatment groups and their corresponding 95% confidence intervals will be obtained. A similar analysis will be used to assess exploratory aims 1 (mood), 2 (side effects), and 3 (craving). Length of time in the study in weeks will be compared between groups using Cox proportional hazards regression (SAS Proc PHREG). Assessments only obtained at baseline and weeks 6 and 12 (e.g. GGT, AST, ALT and CDT levels) or baseline and week12 (e.g. cognitive assessments, neurosteroid and choline levels) will be analyzed using analysis of variance (ANOVA). The correlation between the reduction in alcohol use/alcohol craving and reduction in manic and depressive symptoms, and also improvement in cognitive outcomes, will be assessed using Pearson's or Spearman's correlation coefficient. To address exploratory aim 6) "Determine whether changes in alcohol craving, mood or cognition occur before or after changes in alcohol use." a panel model with lagged effects¹³⁴ will be used to analyze 12-week longitudinal data (SAS Proc Panel) in order to explore serial correlations between changes in alcohol use and depressive symptoms or cognitive outcomes with lagged effect (e.g. one week, two week). The panel model will be constructed for each alcohol use, alcohol craving, depressive and manic symptom, and cognitive outcome and test if change in alcohol use follows changes in craving, mood or cognition at subsequent visits and vice versa.

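### Prespecify a stage factor for the pooled analysis: it costs nothing at the planned 1:1 ratio, and matters only if the drug:placebo ratio is changed after the interim

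*Combined protocol and SAP*

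**What the plan says.** All of the relevant text is in section 3.3.c unless another section is named.

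- Stage 1 allocation (General Analytic Plan): "participants will be randomized at a 1:1:1 ratio to receive one of the three treatments". Under Sample size re-estimation: "we will recruit 99 subjects (i.e., 33 subjects per arm) with 1:1:1 treatment allocation ratio".
- Stage 2 allocation (Sample size re-estimation): "an additional 100 subjects at 1:1 ratio will be recruited at Stage 2". If both drugs do well, three arms continue, with 66 per arm in total.
- Adaptations open after the interim (General Analytic Plan) include "re-estimating the sample size, or a different randomization scheme may be applied as recommended by the independent DSMB". No ratio, limit or consequence for the analysis is attached to this.
- Pooling: "data collected from both stages will be combined for a final analysis".
- Primary model (Statistical Methods): "using Generalized Estimation Equations (GEEs) analysis with a site effect as a cluster". No term for stage or calendar time is named. Tests are two-sided at 0.05.
- Section 3.3.b.4 expects 48 participants a year over both sites and about 4 years 2 months of enrolment.
- Section 3.3.b.5 adds "An exit survey to evaluate participant's perception of in-person vs. virtual visits".

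**The concern.** Pooling two periods of recruitment without a stage term is safe only if drug and placebo have the same share of participants in each period. The plan sets equal shares in its sample-size text, but the General Analytic Plan permits a different scheme and puts no bound on the drug:placebo ratio. If that option were used to put more Stage 2 participants on drug, the drug arm would be weighted towards later recruits. Any change over time in drinking level, case mix or referral source would then be partly read as a drug effect. The primary estimate, its confidence interval and its p-value would shift in the direction of the drift, and nothing in the analysis text would correct for it.

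**Working it through.** **The plan's own figure.** A two-sample t-test with 66 per arm, effect size 0.50 and two-sided 5% has noncentrality 0.50 × √(66/2) = 2.87 on 130 df and power 81.35%. This reproduces the stated 81.4%. The plan's scale is therefore a standardised difference with SD = 1, which is used below.

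**Timing.** At 48 a year, 99 participants take 99/48 × 12 = 24.75 months and the next 100 take 25.0 months. The stages are consecutive. Their mid-points lie at about 12.4 and 37.25 months, roughly 25 months apart.

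**Inputs.** From the plan: 33 per arm in Stage 1, and 100 in Stage 2. Assumed, because the documents give none: drift *d* between stages of 0.3 or 0.5 SD, and Stage 2 splits of 60/40 (3:2), 67/33 (2:1) and 75/25 (3:1) beside the planned 50/50.

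**Formulas.** Let *s* be the share of an arm recruited in Stage 2.

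- Bias = *d* × (s_drug − s_placebo).
- True SE = √(1/n_drug + 1/n_placebo).
- SE reported without a stage term = √(v_drug/n_drug + v_placebo/n_placebo), with v = 1 + d²·s(1 − s).
- Two-sided error = P(Z > 1.96r − b) + P(Z < −1.96r − b), with r = reported SE / true SE and b = bias / true SE.
- Stage-stratified SE = 1/√(w₁ + w₂), with w = n_drug·n_placebo/(n_drug + n_placebo) in each stage.

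**Worked case, 2:1 with d = 0.5.** s_drug = 67/100 = 0.67 and s_placebo = 33/66 = 0.50, so the bias is 0.5 × 0.17 = 0.085 SD. True SE is √(1/100 + 1/66) = 0.1586, reported SE 0.1633, r = 1.030 and b = 0.536. The tails are 6.9% and 0.5%, or 7.5% in total. Stratified SE: w₁ = 16.5 and w₂ = 67 × 33/100 = 22.11, giving 0.1609, which is 1.5% above 0.1586.

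| Stage 2 ratio | s_drug | s_placebo | Fraction of drift entering | Bias at 0.3 / 0.5 SD | Two-sided error at 0.3 / 0.5 SD | SE cost of stage term, no drift |
|---|---|---|---|---|---|---|
| 1:1 (planned) | 0.602 | 0.602 | 0 | 0 / 0 | 4.8% / 4.4% | 0 |
| 3:2 | 0.645 | 0.548 | 0.097 | 0.029 / 0.049 | 5.1% / 5.4% | 0.5% |
| 2:1 | 0.670 | 0.500 | 0.170 | 0.051 / 0.085 | 5.9% / 7.5% | 1.5% |
| 3:1 | 0.694 | 0.431 | 0.263 | 0.079 / 0.132 | 7.4% / 11.6% | 3.5% |

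Three-arm continuation (33 + 33 in every arm) also gives zero bias.

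**Check by simulation** (20,000 trials per scenario, linear model, 0.5 SD drift). Two-sided error without the stage term was 4.5%, 5.6%, 7.2% and 11.4% for the four rows. With the term it was 5.1%, 5.1%, 4.8% and 4.9%, and the bias was about zero.

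**Gain at 1:1.** With drift, the reported SE is 0.1569 (0.3 SD) or 0.1598 (0.5 SD) without the term, against 0.1552 with it. The term recovers about 1% to 3% of the SE.

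These calculations take one outcome per participant. They do not model the repeated-measures GEE or the effect of interim selection on type I error.

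**The case against.** The strongest reply is that no allocation written in the plan produces a bias. Stage 1 is balanced, Stage 2 is set at 1:1, and the three-arm continuation is balanced too. The phrase about a different scheme sits in a list of examples. The decisions that follow it are to stop, to go on with one drug against placebo, or to go on with both, and none alters the drug:placebo ratio. Moving from 1:1:1 to 1:1 is itself a different scheme and may be all that is meant. Section 3.3.b.11 likewise gives dropping an arm as its example of an interim change. Simply deleting the phrase could appear to bar the move that the design needs.

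Most of this stands, and it limits the point to a conditional one. It does not close the gap. The wording sets no limit on the ratio, and the account of adaptive designs in section 3.1 presents less exposure to placebo as an advantage, which is the direction that an unequal allocation would take.

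A reader might infer that the exit survey shows a shift in visit mode between stages. It shows only that both modes were in use, not that the mix differed by stage. A reader might also look at the upper tail alone, which at 2:1 and 0.3 SD drift nearly doubles from 2.5% to 4.9%. The plan's test is two-sided, and there the error is 5.9% against 5%.

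**Conclusion.** A minor, conditional point. With the planned 1:1 ratio in both stages, a common time trend does not bias the pooled drug–placebo comparison, and the test without a stage term errs slightly on the conservative side. A bias needs two things together: a real drift, and a change in the drug:placebo ratio that the plan permits but does not propose. It is then about a tenth to a quarter of the drift over ratios of 3:2 to 3:1. At a 0.5 SD drift, 2:1 and 3:1 give 0.085 and 0.13 SD, about a third and a half of the plan's minimum important effect of 0.25. Both the ratios and the drifts are assumptions.

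A reader might infer that any trend in drinking over the four years would show up as a treatment effect. The documents do not support that: the allocations they specify cancel it. A reader might also worry about comparing a dropped arm, recruited only in Stage 1, with placebo pooled over both stages. That comparison would be exposed, but the plan does not name it as a primary comparison.

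**What to change.** 1. In Statistical Methods, add stage as a fixed factor to the pooled primary and secondary GEE models. Define it by whether the participant was randomised before or after the interim change of allocation, so that drug and placebo are compared within stage and then combined.
2. In the General Analytic Plan, keep the option of "a different randomization scheme may be applied as recommended by the independent DSMB". Add that, apart from dropping an arm, the drug:placebo ratio stays 1:1, or that any change of ratio is analysed only with the stage-stratified model.

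The cost is a sentence or two in the SAP and one degree of freedom. The SE is unchanged at 1:1 without drift and about 1% to 3% smaller at 1:1 with drifts of 0.3 to 0.5 SD. It is about 1.5% (2:1) to 3.5% (3:1) larger only if the ratio is changed and there is no drift. Both additions should be fixed before the interim results are unblinded, since a stage term added afterwards would look data-driven.

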At each stage, a table will show the adverse events (categorized by seriousness, severity, and possible association with study drug) ordered by decreasing frequency for all patients. If appropriate, the incidence rate of adverse events will be compared by Fisher's Exact Test. Special attention will be given to those participants who have discontinued due to adverse events or experienced a serious adverse event. Exploratory analyses such as determining if baseline blood neurosteroid or choline levels predict response and whether changes in these levels are associated with clinical response will be conducted using a mixed model (SAS Proc GLIMMIX) with baseline blood neurosteroid and choline levels as fixed effects. In addition, subgroup analyses with respect to patient demographics and characteristics may be performed as deemed appropriate by the PI and/or biostatistician. Unless otherwise noted, tests of hypotheses are 2-sided and the nominal level of significance will be 0.05.

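### The sample-size re-estimation is called blinded but is triggered by the comparative interim result, and the plan states no resizing rule or final test that shows type I error is controlled

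*Combined protocol and SAP*

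**What the plan says.** All of this stands in section 3.3.c unless noted.

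- **Trigger and label** (General Analytic Plan): "Depending on the results of the interim analysis, blinded sample size re-estimation may be performed per recommendation from the DSMB".
- **What drives the new size** (same section): "Findings from the interim analysis may result in change in sample size required for achieving statistical" significance at a target power. Earlier in the section, on the basis of the interim analysis of the primary outcome, "adaptations such as stopping the trial early, re-estimating the sample size, or a different randomization scheme may be applied" on the DSMB's recommendation.
- **Who sees what** (section 3.3.b.11): the DSMB and its support statistician have access to unblinded information.
- **Planned sizes** (Sample size re-estimation): "we will recruit 99 subjects (i.e., 33 subjects per arm) with 1:1:1 treatment allocation ratio"; then "an additional 100 subjects at 1:1 ratio will be recruited at Stage 2".
- **Stop**: "If neither treatment has an effect size of at least 0.25 at interim analysis then the trial is discontinued". If one drug reaches 0.25, the less effective one is dropped. If both reach 0.50, both continue.
- **Final test**: data from the two stages are combined, and "tests of hypotheses are 2-sided and the nominal level of significance will be 0.05" (Statistical Methods).

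The plan gives no re-estimation formula, target power for the resizing, direction of change, floor or cap. It gives no stage weights, combination test or adjusted critical value.

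**The concern.** Blinded re-estimation normally means that the new size is computed from pooled data without treatment codes, usually the SD or dropout rate. It has little or no effect on type I error, which is why it needs no adjustment. Here the trigger is the drug-versus-placebo comparison, and the recommendation comes from a body that can see it. That is unblinded re-estimation under another name. If the Stage 2 size is a function of the Stage 1 effect, the pooled statistic no longer has its nominal null distribution, and an unadjusted 1.96 cut-off is not guaranteed to hold its level.

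At stake is whether a positive result would stand. After a resize, a critic could point out that the SAP called the step blinded while its own text shows a comparative trigger, and that nothing in the final test allows for this.

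**Working it through.** **1. The plan's own figure.** For effect size 0.50, the plan states: "we will have 81.4% power with 66 participants per arm". With n = 66 per arm, the noncentrality is 0.50 × √(66/2) = 2.87. A two-sided 0.05 t-test then gives 81.35% (normal approximation 81.9%). The figure reproduces as a fixed-size, single-comparison calculation. It includes no adaptation.

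**2. Inputs.** From the plan: Stage 1 with 33 per arm; Stage 2 with 50 per arm if two arms continue (100 at 1:1), so 83 per arm at the end; stop at 0.25; two-sided 0.05, that is 2.5% in the favourable direction. Assumed, because the plan is silent: the resizing rule, its floors and caps, a normal outcome with known variance, and no dropout.

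**3. Assumed rule.** Final N per arm = 2 × ((1.96 + 0.84)/d)², where d is the observed Stage 1 effect. Stage 2 size is n₂ = N − 33, held within the stated limits. N equals the planned 83 at d = 2.80 × √(2/83) = 0.43. Smaller observed effects enlarge Stage 2 and larger ones shrink it.

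**4. Hand check.** Under the null, given d, the chance that the pooled test is significant in the drug's favour is 1 − Φ[(1.96√(33 + n₂) − 33d/√2)/√n₂].

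| Observed d | n₂ under the rule | Chance at fixed n₂ = 50 | Chance at resized n₂ |
|---|---|---|---|
| 0.25 | 251 − 33 = 218, capped at 100 | 1 − Φ(1.700) = 4.5% | 1 − Φ(1.677) = 4.7% |
| 0.40 | 98 − 33 = 65 | 1 − Φ(1.205) = 11.4% | 1 − Φ(1.249) = 10.6% |
| 0.50 | 63 − 33 = 30 | 1 − Φ(0.875) = 19.1% | 1 − Φ(0.710) = 23.9% |

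Enlarging adds a little near the 0.25 boundary and removes more from about 0.30 to 0.43. Shrinking after a large observed effect adds clearly.

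**5. Whole design.** Simulation of 3 million null trials, better drug kept, pooled z-test at 1.96. One-sided false benefit, nominal 2.5%:

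| Stage 2 per arm | 0.25 stop obeyed | Stop not obeyed |
|---|---|---|
| Fixed 50 | 3.0% | 3.9% |
| Increase-only, 50–100 | 2.9% | 4.2% |
| Increase-only, 50–200 | 2.9% | 4.4% |
| 40–100 | 3.1% | 4.4% |
| 25–100 | 3.5% | 4.7% |
| 10–100 | 3.9% | 5.2% |
| 10–200 | 3.9% | 5.4% |

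Total two-sided error (nominal 5%) is at most 3.9% in these rows with the stop obeyed. Without the stop it is 5.0% at fixed size and up to 7.0%. Three-arm continuation, reached in about 0.4% of null trials, is left out of the table; including it moves the fixed, stop-obeyed figure from 3.0% to 3.1%.

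**6. Separating resizing from selection.** With one drug against placebo and no stop, the error is 2.5% at fixed 50, 3.1% increase-only to 200, and 3.6% with 10–200. Resizing therefore has a cost of its own in that setting. In the two-drug design, the step from 2.5% to 3.0% or 3.9% at fixed size is the cost of picking the better drug.

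**7. Effect of weighting.** With stage weights fixed at 33:50, every resizing rule returns to the fixed-size value, 3.0% (stop obeyed) or 3.9% (not obeyed). Adding a closed Dunnett test for the two drugs brings this to 2.1% and 2.5%.

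**The case against.** A reader might infer that the re-estimation necessarily raises the false-positive rate. The documents do not support that. The stop is worded as mandatory, and under it increase-only resizing leaves the error at 2.9% against 3.0%. The rise to 3.9% needs Stage 2 to shrink to 10 per arm, which no passage describes; the plan gives 100 further participants. The figures above 4% need the stop to be set aside, a departure from its wording. With the stop obeyed, total two-sided error stays under 5% in every case run. These points stand.

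They do not settle the matter, because the plan commits to neither condition. It speaks of a change in sample size, not an increase. It calls the interim rules principles, also refers continuation to a precision analysis, and has interim decisions made in consultation with the program official and the DSMB.

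A benign reading of the label is also possible: site staff stay masked, or the interim result only decides whether to resize and the calculation uses pooled variance. The documents say neither, and in both cases the trigger would still be comparative.

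**Conclusion.** The label is wrong as written, and type I error control after resizing is not shown. This is established by the text alone. The size of any inflation is not established, since it depends on direction, limits and whether the stop binds. Under the assumed 80%-power rule, resizing changes one-sided false benefit by about −0.1 point (stop obeyed, increase-only) to +0.9 point (stop obeyed, Stage 2 down to 10). If the stop is not obeyed, the change is +0.3 to +0.5 point increase-only and up to +1.5 points with shrinking (5.4% − 3.9%). The excess over 2.5% already present at fixed size belongs to arm selection and should be dealt with as its own issue. The change is worth making because it is cheap and can be made before any unblinding.

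**What to change.** Choose one.

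**(a) Make it truly blinded.** Compute the new size once, from the pooled, arm-masked SD and dropout, before the comparative interim results are seen. Allow increases only, with a stated cap, and delete the opening clause that ties the step to the interim results. Cost: effect-driven resizing is given up. Arm selection still needs its own adjustment.

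**(b) Keep it unblinded and protect the test.** Delete the word 'blinded' and state the formula, target power and limits. Combine stage-wise statistics with weights fixed in advance from the planned stage sizes: 33:50 on the two-arm path and 33:33 on the three-arm path (66 per arm). If the month-34 rule forces an early interim, set the weights from the actual Stage 1 size before Stage 2 starts. Add a closed Dunnett-type adjustment for arm selection, because the weights alone leave 3.0% to 3.9%. Cost: slight loss of efficiency.

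Either option is a change of SAP wording.
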